**Justification for Number of Subjects or Data:**

Sample size estimate suggest that 1031 participants are required.

The primary outcome measure for the power calculation is the difference of intubation rate between intervention arm (systemic anticoagulation using enoxaparin subcutaneous (or unfractionated heparin) and control arm (current standard care). We expect the intervention arm will provide a reduction by 30%. The baseline intubation rate was estimated 25 % in the control arm. Assuming alpha at two-sided 0.05 and power at 80% indicates that a total sample size of 1031participants (687 in the intervention and 344 in the control arm) would be required.

Required sample sizes	
Assuming 80% power, alpha=0.05 and two-sided testing	
Reduced by	Estimated intubation rate in COVID-19 inpatients with standard care
10%	10181 (6787:3394)
20%	2435 (1623:812)
30%	1031 (687:344)
40%	548 (365:183)
50%	329 (219:110)

## **Randomization**

Participants will be randomly assigned in a 2:1 ratio to the intervention or standard care control arm. Randomization will be stratified by stable/non-stable status and creatinine clearance rate. The allocation sequence will be generated using random permuted blocks within stratum. Using restricted randomization within the stratum ensures that number of participants is balanced between study arms within stratum and the stratification factors will be balanced in each study arm.

**Appendix 1:**

HFHS – Tier 1: Heparin Induced Thrombocytopenia (HIT) Guidelines -(MMC-08):  
Bivalirudin Criteria for use in patients with suspected or confirmed HIT.

**Dosing for HIT**

Therapeutic Range (goal) of the aPTT Value:

- The therapeutic range is an aPTT value 1.5-2.5 times the patient’s baseline aPTT value.
- If no baseline aPTT value is available, use 29 seconds as the baseline value.
- The upper range should not exceed 100 seconds.

[figure not shown]

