        - b. CrCl  $\geq$  30: Rivaroxaban 15 mg PO BID x 15 days, then 20 mg PO QD

- c. CrCl < 30: Apixaban 5 mg PO BID
  2. *Option for unstable patients (anticipated procedures, hemodynamically unstable, severe critically illness):*
    - a. Bivalirudin – goal PTT 1.5-2.5 times baseline PTT; dosing and monitoring per the HFHS HIT Guidelines. (Appendix A)
      - i. CrCl >60 mL/minute: 0.15 mg/kg/hr
      - ii. CrCl 30 to 60 mL/minute: 0.08 mg/kg/hr
      - iii. CrCl <30 mL/minute or dialysis: 0.05 mg/kg/hr
      - iv. CRRT: 0.07 mg/kg/hr
    - b. Suspected or confirmed heparin induced thrombocytopenia with thrombosis (HITT):
      - i. Treat patient for 3 months with one of the following options given the clinical scenario:
        1. *Stable patients (no procedures, hemodynamically stable):*
          - a. CrCl < 30: Apixaban 10 mg PO BID, then Apixaban 5 mg PO BID thereafter
          - b. CrCl ≥ 30: Fondaparinux
            - i. Weight < 50 kg: 5 mg SubQ Daily
            - ii. Weight 50-100 kg: 7.5 mg SubQ Daily
            - iii. Weight > 100 kg: 10 mg SubQ Daily
          - c. CrCl ≥ 30: Rivaroxaban 15 mg PO BID x 15 days, then 20 mg PO QD
        2. *Unstable patients (anticipated procedures, hemodynamically unstable, severe critically illness):*
          - a. Bivalirudin: goal PTT 1.5-2.5 times baseline PTT; dosing and monitoring per the HFHS HIT Guidelines
            - i. CrCl >60 mL/minute: 0.15 mg/kg/hr
            - ii. CrCl 30 to 60 mL/minute: 0.08 mg/kg/hr
            - iii. CrCl <30 mL/minute or dialysis: 0.05 mg/kg/hr
            - iv. CRRT: 0.07 mg/kg/hr
  9. The patients will be monitored after the initiation of therapy.
    - a. The first follow-up will be twelve hours after the start of anticoagulation.
    - b. Evaluation of clinical status will be completed twice daily to monitor progression of hypoxemia, respiratory failure, development of ARDS.
    - c. Daily laboratory testing including CBC with differential, electrolytes, PT, aPTT, INR, D-Dimer.
    - d. Ferritin, LDH, Triglycerides will be checked QOD as per Henry Ford Hospital COVID-19 Management guidelines.
  10. All patients who are in the control group will receive standard of care therapy inclusive of VTE prophylaxis and proning if part of routine care.

11. Post-discharge follow-up:
  - a. Patients will be maintained on anticoagulation upon discharge.
  - b. Patient contact 2 weeks post discharge
  - c. D-Dimer to be drawn at 4 weeks

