**Table 2. Bivalirudin maintenance infusion dose adjustment**

PTT (seconds)	Dose Adjustment	Monitoring
< 1.5 x baseline	Increase infusion by 20%	Recheck PTT 2 hours after rate change
1.5 – 2.5 x baseline	Continue current rate	Recheck PTT in 4 hrs; if within therapeutic range 2 consecutive times, check PTT every 12 hrs
> 2.5 – 3 x baseline	Decrease infusion by 20%	Recheck PTT 2 hrs after rate change
> 3 x baseline	Hold for 1 hour, then restart at 50% lower rate	Recheck PTT 2 hrs after rate change

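### The 100-second aPTT ceiling in Appendix 1 is missing from the bivalirudin adjustment table, so for a baseline aPTT above 40 s the table's no-change row covers values the ceiling excludes

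*Protocol*

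**What the plan says.** Three places in the protocol bear on the aPTT goal for bivalirudin.

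- **Appendix 1, Dosing for HIT.** The goal is relative to the patient: "The therapeutic range is an aPTT value 1.5-2.5 times" the patient's own baseline. A default covers a missing value: "If no baseline aPTT value is available, use 29 seconds as the baseline value". An absolute limit follows: "The upper range should not exceed 100 seconds".
- **Appendix 1, Table 2.** Four rows turn a PTT into an action. Below 1.5 times baseline: "Increase infusion by 20" per cent. From 1.5 to 2.5 times: "Continue current rate". Above 2.5 and up to 3 times: "Decrease infusion by 20" per cent. Above 3 times, the infusion is held for an hour and restarted at half the rate. The first column is labelled in seconds, but every entry is a multiple of baseline and none mentions 100 s. The no-change row also sets monitoring: after two successive in-range values, checks move from 4-hourly to 12-hourly.
- **Study Procedure, step 8.** For unstable patients, both with and without thrombosis, the instruction is "goal PTT 1.5-2.5 times baseline PTT; dosing and monitoring per the HFHS HIT Guidelines". Neither entry gives a limit in seconds.

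**The concern.** A relative goal and an absolute ceiling can coexist only if the instruction that staff act on says what happens where they part. Table 2 is that instruction, and it omits the ceiling. For some baselines, one aPTT value is therefore in range by the table and out of range by the goal definition shortly above it.

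The ceiling can bind only where 2.5 times baseline exceeds 100 s, which is exactly where the table ignores it. Two things are left unclear for such a patient: whether the rate should change, and whether checks may be spaced to 12 hours. The setting is anticoagulation of unstable patients with suspected or confirmed HIT, in a trial that records major bleeding as an adverse event. The point concerns safety conduct. It does not touch the primary endpoint, the sample size or the analysis.

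**Working it through.** **Inputs.** From Dosing for HIT: goal multiples 1.5 and 2.5, default baseline 29 s, ceiling 100 s. From Table 2: row boundaries 1.5, 2.5 and 3 times baseline. I take PTT in Table 2 and aPTT in the goal definition to be the same test. The ceiling is a stated limit, so there is no derived figure to reproduce first.

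**Thresholds.** A row boundary at multiple m reaches the ceiling when baseline = 100 / m.

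- Top of the no-change row: 100 / 2.5 = 40.0 s.
- Top of the increase row: 100 / 1.5 = 66.7 s.

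**Row boundaries by baseline (all in seconds).**

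| Baseline | 1.5 × | 2.5 × | 3 × | No-change row over 100 s | Increase row over 100 s |
|---|---|---|---|---|---|
| 29 (default) | 43.5 | 72.5 | 87 | none | none |
| 40 | 60 | 100 | 120 | none | none |
| 45 | 67.5 | 112.5 | 135 | above 100 to 112.5 | none |
| 50 | 75 | 125 | 150 | above 100 to 125 | none |
| 60 | 90 | 150 | 180 | above 100 to 150 | none |
| 70 | 105 | 175 | 210 | 105 to 175 | above 100 to below 105 |

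The excess of the table's upper goal over the ceiling is 2.5 × baseline − 100: 12.5 s at a baseline of 45 s and 25 s at 50 s.

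**Effect on monitoring.** Take a baseline of 45 s and two successive values of 110 s. Since 110 / 45 = 2.44, both fall in the no-change row, and on that row's boundaries the checks move to 12-hourly. By the ceiling, both values are out of range.

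**Does reading the ceiling into the table resolve it?** Suppose the in-range band is taken as 1.5 × baseline up to the smaller of 2.5 × baseline and 100 s. At a baseline of 50 s the band becomes 75 to 100 s. A value of 110 s is then above the band, but the decrease row starts only above 125 s, so no row applies. Above a baseline of 66.7 s the band is empty, because its lower end (1.5 × baseline) already exceeds 100 s. The gap remains under this reading.

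**The case against.** The strongest reply is that the ceiling belongs to the definition of the therapeutic range. Table 2 uses that term, and step 8 sends dosing and monitoring to the same guideline. On this view the omission is a missing cross-reference, not a second rule. That reading is reasonable and may be what was meant. It does not finish the job, because values between 100 s and 2.5 times baseline are then left without an action. A figure in this part of the appendix is not shown and the full institutional guideline is not at hand, so the ceiling may be handled there. The printed table still does not carry it.

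Several stronger readings are tempting, and the documents do not support them.

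- A reader might infer that staff are told to keep or raise the rate above 100 s whenever baseline exceeds 40 s. The increase row needs a baseline above 66.7 s. Between 40 and 66.7 s only the no-change row is affected, so it is also too strong there to say that the two rules point in opposite directions.
- A reader might infer that baselines of 55 to 75 s are to be expected, because that is the aPTT target of the study heparin infusion in step 6. This assumes that an aPTT drawn on heparin is used as baseline, which the text neither allows nor rules out. On that assumption the upper goal would be 137.5 to 187.5 s, or 37.5 to 87.5 s above the ceiling. However, aPTT is on the laboratory list and laboratories are reviewed at enrolment, so a value from before heparin should often exist.
- A reader might take the Background as evidence of high baseline aPTT. It reports a prolonged prothrombin time and does not mention aPTT. Step 6 pairs 1.5 to 2.5 times normal with 55 to 75 s, which implies a normal value of 75 / 2.5 = 30 s to 55 / 1.5 = 36.7 s, below the 40 s threshold.
- A reader might infer that excess major bleeding would follow. No figure in the protocol allows that to be estimated.

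**Conclusion.** The point holds in a limited form. The goal definition in Appendix 1 carries a 100 s ceiling that no row of Table 2 and neither bivalirudin goal in step 8 repeats. For a baseline above 40 s, the no-change row, with its move to 12-hourly checks, extends past the ceiling up to 2.5 times baseline. For a baseline above 66.7 s, the increase row does so as well. At or below 40 s, including the 29 s default, there is no conflict.

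The arithmetic rests only on the protocol's own multiples and ceiling. How often it matters is not known. A patient must have suspected or confirmed HIT, be treated with bivalirudin, have a baseline above 40 s, and then have an aPTT above 100 s but within the table's no-change or increase band. The number is probably small. The point merits correction because it leaves an anticoagulant instruction unclear and costs almost nothing to settle.

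**What to change.** Reconcile the goal definition in Dosing for HIT, Table 2 and the two bivalirudin entries in step 8, so that every aPTT value maps to one action and one recheck interval once both the multiple and the ceiling are applied. One way to show this is a column in absolute seconds beside the multiples. State also whether an aPTT drawn during or shortly after study heparin may serve as the baseline. Which limit governs, and what is done above it, is for the sponsor's clinical and pharmacy team to decide.

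The cost is a wording change to one table, the step 8 entries and the definition of baseline. It adds no patients, visits or tests, and leaves the statistical design unchanged.

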**Table 1. Bivalirudin initial dosing**

Bivalirudin Initial Dosing (250 mg/50 mL NS or D5W)		Monitoring
CrCL (ml/min)	Dose (mg/kg/hr) – based on actual weight. Max: 150 kg	
> 60	0.15 mg/kg/hr	Draw first aPTT 2 hours after the initiation of the infusion.
30 - 60	0.08 mg/kg/hr	
< 30/iHD	0.05 mg/kg/hr	
CRRT	0.07 mg/kg/hr	

**Table 2. Bivalirudin maintenance infusion dose adjustment**

PTT (seconds)	Dose Adjustment	Monitoring
< 1.5 x baseline	Increase infusion by 20%	Recheck PTT 2 hours after rate change
1.5 – 2.5 x baseline	Continue current rate	Recheck PTT in 4 hrs; if within therapeutic range 2 consecutive times, check PTT every 12 hrs
> 2.5 – 3 x baseline	Decrease infusion by 20%	Recheck PTT 2 hrs after rate change
> 3 x baseline	Hold for 1 hour, then restart at 50% lower rate	Recheck PTT 2 hrs after rate change

**Figure 1. Transitioning to warfarin: Bivalirudin conversion to warfarin**

- Due to the affinity for thrombin, all DTI interfere with functional clotting assays (PT/INR). Among the commercially available DTI's the prolongation of the INR by bivalirudin is less than that seen with that of argatroban. Evidence suggests that bivalirudin's effects INR by elevating it by approximately 0.5 over the course of therapy initiation and decreases the INR by 0.5 on bivalirudin discontinuation. (11)
- In order to predict the INR on warfarin alone, temporarily discontinue bivalirudin until its anticoagulant effect has resolved (usually for 4 to 6 hours or until the PTT is returned to baseline) then follow Figure 1.
- If the repeat INR is below the desired therapeutic range, resume the infusion of bivalirudin and adjust warfarin dose accordingly; Repeat the procedure daily until the desired therapeutic range on warfarin alone is reached.

**Table 3. Transitioning between parenteral anticoagulants in HIT/HITTS**

From	To	Action
Fondaparinux Therapeutic dose	Bivalirudin	
 
• Discontinue fondaparinux
 
• Initiate bivalirudin when next fondaparinux dose is expected to be given (24 hours from last given dose)
 

Fondaparinux Prophylactic dose	Bivalirudin	
 
• Discontinue fondaparinux
 
• Initiate bivalirudin as clinically indicated irrespective of time of last given fondaparinux dose
 

Bivalirudin Without renal	Fondaparinux	
 
• Discontinue bivalirudin drip
 
• Initiate fondaparinux immediately
 

Bivalirudin With renal impairment	Fondaparinux	
 
• Discontinue bivalirudin drip
 
• Initiate fondaparinux once PTT is 2 times the baseline
 

